**Table 1. Study Timetable**

Preparation (3 months)	Implementation (12 months)	Evaluation (6 months)
Clinic Selection Baseline Data Collection (a 12 month look-back) Clinic Randomization	Staff Training in All Clinics at baseline and one month. Data collection and monthly Performance Feedback in all 24 Clinics (both Paper F2Q and eReferral Clinics)	Data Analysis Manuscript preparation Health system Feedback and Dissemination

**Table 1A. 2/28/2017 Amendment Pilot Study Timetable**

Preparation (2-4 months)	Implementation (6-9 months)	Evaluation (2-4 months)
Clinic Selection Baseline staff survey	Staff Training in 1-3 Clinics at baseline and one month. Data collection and monthly Performance Feedback in all clinics	Data Analysis Manuscript preparation Health system Feedback and Dissemination

**Clinic Eligibility Requirements:** The following specific inclusion criteria will be used to establish clinic eligibility: the presence of discrete primary care clinical services within the clinic (defined as general internal medicine or family medicine clinical services); at least three primary care clinician providers in the clinic (physicians or nurse practitioners/physician assistants who see patients independently of a physician); a total primary care clinical volume of at least 60 patients each week; an existing EHR requirement for staff to document tobacco use status including smoking status on all adult patients visiting the clinic at every visit; a capacity to enumerate patient visit information including adult patients/month and adult tobacco users/month by clinician and by clinic; a willingness to participate in the proposed research; a lead physician or a clinic manager on site who agrees to serve as a clinic champion for the project; and, a willingness to accept random assignment to either of the two experimental conditions.

2/28/2017 Amendment. The clinic eligibility for the SmokefreeTXT eReferral pilot will be the same as those for the existing protocol, such that clinics must have at least three clinicians serving at least 15 patients per week. The clinics must be using an EHR to document patient smoking status at every visit and must be able to share information about the flow of adult tobacco using patients (i.e., a denominator for analyses of eReferral rates) seen in the clinic in each of the 6-9 months of the active eReferral period. Clinic leaders must agree to participate in this quality assurance evaluation activity. Clinics will not be required to agree to randomization, as that is not part of this pilot study.

**Clinic Selection:** Once WF, GHS, and UW-CTRI identify eligible clinics based on inclusion criteria from the potential clinics in the each system, UW-CTRI staff (Study PI Physician [[name]] and one other staff person) will meet with both the physician leader and clinic manager. During this brief meeting, inclusion criteria will be confirmed and the study will be described in detail including the two randomization arms and the approximate date of initiation of the intervention. These will continue until 13 clinics from each system meeting inclusion criteria have been identified and agree to participate.

2/28/2017 Amendment: As in the existing protocol, Study PI [name] and one other research staff person will reach out to the physician leader and clinic manager at 1-3 clinics meeting the eligibility criteria specified above. Inclusion criteria in terms of provider numbers and patient flow will be confirmed and the study timeline, training and assessment activities, and eReferral workflow will be discussed in detail.

**Baseline Data Collection:** Prior to initiating the Intervention Phase of the study, an EHR-based look-back process will be used to collect 12 months of baseline data from the selected clinics that had previously used F2Q. These 12 months of clinic ascertainment baseline data will include: information on adult patients and adult tobacco users seen in the clinic; rates of quitline referrals via existing F2Q programs; and, rates of quitline engagement for those fax-referred for services (the rate of “quality referrals”). Clinic staff will not be informed that baseline data will be collected prior to the start of the intervention in an effort to minimize changes in clinician WTQL referral behavior prior to the intervention.

2/28/2017 Amendment. Prior to eReferral launch, staff in each clinic will be asked to complete a brief, anonymous survey regarding their knowledge of, current practices, and attitudes toward tobacco dependence treatment and SmokefreeTXT. Baseline data collection is not relevant to SmokefreeTXT eReferral, so we will not request aggregate historical EHR records regarding this, as we expect this to be near zero in clinics and because there is no clearly identified field in which such a referral would be recorded.

**Clinic Randomization:** Once each of the 2 sets of 12 clinics are identified and agree to participate, they will be stratified within each health system and randomized into the two study conditions using Urn randomization (NOTE: one clinic from each system will serve as an eReferral pilot clinic to test the eReferral technology). In this methodology, the project MATCH randomization beta program will be used to equate the two clinic groups with respect to three factors: approximate number of primary care providers, approximate smoking prevalence amongst the adult patients seen during the one-year baseline period, and approximate rate of F2Q referral for all tobacco users seen during the baseline period. Each of the 24 identified clinics will be randomized into one of the following two intervention conditions: a) six per health system to continue with the existing F2Q WTQL referral system (Fax to Quit) and b) six per health system to transition to an EHR-based WTQL referral system (eReferral)

2/28/2017 Amendment. The 1-3 clinics for pilot testing of SmokefreeTXT eReferral will not be randomized; all will receive access to the EHR eReferral tools for 6-9 months during the study.

**Implementation Phase:** The following activities (with associated key outcomes) will take place over the twelve months of the Implementation Phase in each of the two study conditions (Table 2):

**Table 2. Intervention Activities and Outcomes**

Intervention	Activities	Key Outcomes
Fax Referral – Fax to Quit Condition (12 clinics)	✓ On site Baseline training (30 minutes) for all clinical staff describing the Wisconsin Tobacco Quitline (WTQL) and its services, which tobacco users are appropriate for a WTQL referral, and workflow for use of that clinic's condition-	✓ Monthly total of adult patient visits to the clinic as well as number and proportion of those adults who report on that clinic visit that they are current tobacco users
eReferral Condition (12 clinics)		
NOTE: apart from their different referral mechanisms, the intervention training,		

feedback, and other activities will be identical for the two intervention conditions	
 
✓ specific WTQL referral mechanism (either F2Q or eReferral)
 
✓ One week post-intervention launch meeting with clinic manager and physician champion to assess the launch and program
 
✓ Monthly aggregate reports sent to clinic contact indicating percentage and volume of tobacco user referred by that site; and number of patients referred who engaged in WTQL services
 
✓ Referral refresher trainings at one month
 
	
 
✓ Percentage and number of patients who smoked referred to the WTQL
 
✓ Number of referred patients who engage in tobacco telephone quitline services
 
✓ Baseline and 6 month post-intervention staff satisfaction regarding the WTQL referral
 
✓ 4 month post-quitline registration date quit rate
 

--	---	--

**Table 2A. 2/28/2017 Amendment. Intervention Activities and Outcomes**

Intervention	Activities	Key Outcomes

eReferral Condition (1-3 clinics)
 
NOTE: providers in all clinics will be encouraged to continue to address tobacco use with all patients in accordance with best practices. The study intervention will be to turn on an EHR eReferral tool to connect adult patients who smoke and who want to quit in the next 30 days to a fee-free text-message support program, SmokefreeTXT
	
 
✓ On site Baseline training (30 minutes) for all clinical staff describing SmokefreeTXT services, which tobacco users are appropriate for a SmokefreeTXT referral, and eReferral workflow
 
✓ One week post-intervention launch meeting or call with clinic manager and physician champion to assess the launch and program
 
✓ Monthly aggregate reports sent to clinic contact indicating percentage and volume of tobacco user eReferred to SmokefreeTXT by that site; and number of patients referred who engaged in
 
	
 
✓ Monthly total of adult patient visits to the clinic as well as number and proportion of those adults who report on that clinic visit that they are current tobacco users
 
✓ Percentage and number of patients who smoked and had text-capable phones referred to SmokefreeTXT
 
✓ Number of referred patients who enroll in SmokefreeTXT
 
✓ Baseline and 6-9 month post-intervention staff satisfaction regarding SmokefreeTXT eReferral
 
✓ 6 week post-target quit date quit rate
 

	✓ SmokefreeTXT services eReferral refresher trainings at one month	
--	--	--

**Baseline Training Activities:** The following information will be conveyed to all staff during the 30 minute baseline training. Apart from details regarding use of the F2Q vs the eReferral WTQL referral process, all training activities will be identical for the two intervention conditions:

- Providing an overview of the tobacco telephone cessation services – the WTQL
- Demonstrating how the F2Q or eReferral WTQL referral mechanism can be integrated into clinic workflow
- Emphasizing that the WTQL is a supplement to, and not a substitute for, their clinical tobacco cessation intervention
- Providing a step-by-step approach to using F2Q or eReferral with patients including the use of the necessary technology and EHR documentation
- Providing instructions on how to obtain patient informed consent for either F2Q or eReferral
- Describing which adult patients will be good candidates for a referral for WTQL services (i.e., “a quality referral”)
- Offering resource materials and hand-outs to promote the WTQL
- For the clinic manager only, a telephone number and e-mail address to contact study staff with any problems in the implementation or continuation of F2Q or eReferral at their site.

2/28/2017 Amendment. As in the existing protocol for Quitline referral, SmokefreeTXT pre-launch training will provide an overview of the SmokefreeTXT program as a treatment extender (not substitute) and will review the SmokefreeTXT eReferral workflow and provide step-by-step guidance in the eReferral process, including how to assess readiness to quit and obtain patient consent. At the training, the clinic manager and identified clinic champion (if different from the clinic manager) will be given a study number and e-mail address for support and assistance regarding SmokefreeTXT eReferral.

#### **Additional Training provided at Baseline Training for Clinic Managers including Implementation**

**Manual:** As part of the 30 minute baseline training, each clinic manager will receive a paper and electronic copy of the UW-CTRI manual for implementing either F2Q or eReferral in the clinic. That manual already exists for the F2Q condition, as it has been used over the last decade for Wisconsin clinics that have implemented this WTQL referral option (“Fax to Quit Manual: A Step-by-Step Guide for Healthcare Organizations”). That existing F2Q manual will be adapted for the eReferral condition clinics. The manual is designed to be a self-guided implementation tool for health systems for referring patients who use tobacco to the WTQL. The manual includes all required forms including for the F2Q condition a specific F2Q enrollment form personalized to the clinic that must be faxed to the quitline in order to link an interested patient to the WTQL (Figure 2) for the F2Q sites. For the eReferral condition, there will be an essentially identical EHR –based form for WTQL referrals. Also included in the manual is a “Fax to Quit Flow Chart” (Figure 1). All 24 clinic sites (fax and EHR-based referral clinics) will be urged to follow this flow chart (title will be adapted for eReferral condition) as they integrate tobacco quitline referral into the regular workflow of patient care. Effective use of the WTQL referral programs (both F2Q and eReferral) will be guided via this flowchart and requires two key components: a) a few simple systems-level changes in clinic operations to ensure that the tobacco quitline option is consistently offered to

tobacco users, and, b) a commitment by clinician and support staff to integrate these operational steps into their clinic workflow.

2/28/2017 Amendment. As in the existing protocol, clinic managers will be given paper and electronic copies of a UW-CTRI manual for eReferral. This manual will reflect the nature of the SmokefreeTXT program and the specific workflow for eReferral to this texting service.

In terms of the specific flow chart steps (Figure 1), the foundation of the program is a clinic-wide system to assess tobacco use status as a regular part of the vital signs ascertainment, typically determined and documented by the Medical Assistant (MA) or other clinic staff who “rooms” the patient (the person who brings the patient from the waiting room to the examination room). Once the patient is brought to the examination room, the MA typically collects and documents the vital signs (blood pressure, pulse, temperature, and respiratory rate). With the advent of the Federal Meaningful Use EHR Incentive Program, nearly all EHR vendors, and healthcare systems also collect and document tobacco use status on each patient. At this point, workflow processes diverge based on whether the clinic was randomized to the F2Q or the eReferral condition.

2/28/2017 Amendment. The workflow for SmokefreeTXT eReferral is similar to that of Quitline referral in the existing protocol. The first, foundational step is for “Roomers” who assess vital signs to assess and record smoking status in the EHR. Only clinics in which this is already standard protocol will be eligible for this pilot study. As such, this step in the workflow will reflect current practice rather than a change in the clinics to be studied.

**Tobacco User Referral in F2Q condition:** If a patient is identified as a current tobacco user, the MA will leave a clinic-specific (to allow for ascertainment of clinic-specific referral rates) F2Q form (Figure 2) in the exam room to prompt the clinician to address the topic. Importantly, once tobacco use status is documented, the clinician will be asked to address tobacco dependence only with clinic patients who use tobacco - about 17% (based upon the current smoking prevalence rate among adults in Wisconsin). The F2Q protocol then requires the clinician to advise each tobacco user to quit and assess the patient's willingness to quit within the next 30 days. If unwilling, the clinician ends the tobacco cessation discussion at that point, offering the tobacco user a WTQL card or brochure and motivational counseling to consider quitting in the future. If the patient expresses a willingness to try to quit over the next 30 days, the clinician recommends a prescription for an FDA-approved cessation medication and offers telephone counseling through the WTQL. If the tobacco user is willing to accept counseling from the quitline s/he is asked to sign the simple F2Q form at the end of the clinic visit, consenting to the referral and the exchange of information, providing two telephone numbers and best times to call. The form is then passed to the MA (part of the visit closure workflow procedures) who then faxes the form to the WTQL. The WTQL then makes at least five attempts to proactively contact the patient by telephone over the next three days. If a successful contact is made and the patient agrees to WTQL treatment services, evidence-based counseling and over-the-counter nicotine replacement medication is then provided to the patient (via the telephone and via a mailing with additional self-help quitting materials). Finally, the WTQL faxes back to the clinician the outcome of the telephone contact.

The F2Q program is designed to be of minimal burden to the clinic and staff, requiring about 30 seconds of time by the MA when rooming each patient, and about two to three minutes of clinician time for the approximately 17% of adult patients who use tobacco. Our experience in Wisconsin has demonstrated that clinics are willing to adopt the program because it is viewed as a modest time commitment and a free, value-added service for their patients.

The F2Q form (Figure 2) is an essential document for the successful use of F2Q. This form provides key information on both the patient and the clinician so that the quitline can proactively contact the patient and then give the clinician feedback on efforts to contact the patient and services used. This WTQL feedback for each referred patient is faxed back to the patient's clinic. As shown on Figure 2, F2Q is intended for use only with tobacco users who indicate they want to make a quit attempt within the next 30 days. This criterion is an effort to refer "quality contacts" - tobacco users interested in quitline counseling.

In addition to patient-specific information (primary and secondary telephone number, language preference, type of tobacco used, best time of the day to call, and consent to receive a call from the quitline and share follow-up information with clinician), the F2Q form includes specific contact information for the patient's clinician. The purpose of this contact information is to provide feedback to the clinician regarding whether the quitline was able to contact the patient, and which service options the quitline provided to the tobacco user (self-help materials, over the counter nicotine replacement therapy, referral to a local cessation program, enrollment in the quitline counseling, readiness to quit, and quit date). Finally, F2Q forms are personalized to each clinic and to each clinician so the source of each referral can be adequately tracked and assigned to the appropriate source of the referral.

2/28/2017 Amendment. There is no fax-to-quit enrollment mechanism for SmokefreeTXT.

**Tobacco User Referral in eReferral Condition:** The EHR-based, fully electronic bi-directional referral (eReferral) condition involves all of the procedures and resources used in the F2Q condition above. In addition, the following workflow will be followed for the eReferral clinic site (Figure 3). Once the MA has identified a patient as a tobacco user, the EHR will be programmed to prompt the WTQL eReferral Best Practice Advisory (BPA). A BPA is an EHR-based functionality that prompts clinical interventions and provides clinical decision support (CDS) once certain clinical conditions have been met (in this instance, upon a patient being identified as a current tobacco user, the BPA prompt appears, driving the clinical staff to click on it and consider the recommended clinical activities prior to the completion of that clinic visit). In this instance, the eReferral manual will inform clinic staff of a workflow modification requiring that, in response to a WTQL eReferral BPA, the MD, NP, or PA should assess the patient's willingness to quit, and for those willing, should discuss potential cessation medications, and offer the patient a referral to the WTQL for more in-depth support/counseling. If the patient is interested in support from the WTQL, the clinician records in the EHR the patient's verbal consent for the referral and exchange of information (Yes/No box), selects the best time for the quitline to call the patient (drop-down menu). Upon completion of these minimal EHR actions, the clinician then places "the order", an electronic request to the WTQL to contact the patient for quitline treatment services. This order is electronically transmitted to the WTQL and includes patient demographic information so that the quitline can contact the patient. As with F2Q, the quitline will make five attempts to contact the patient. Once the WTQL completes treatment or exhausts the call attempts, they electronically send the eReferral service data back to the patient's EHR, which automatically populates the patient's EHR in two places – data on patient contact, counseling provided, and quit date are saved as a "referral outcome note" (Figure 5), while provision of over-the counter nicotine replacement medication mailed to the patient (including the medication start and end dates based on the quit date) is documented in patient's EHR as part of the patient's medication list (Figure 5).

2/28/2017 Amendment. As with eReferral to the telephone Quitline, eReferral to SmokefreeTXT will be a fully electronic, "closed-loop" referral in which the outcome of the referral is automatically fed back

into the patient's EHR 6 weeks after the target stop-smoking date. When a "Roomer" documents that a patient is currently a smoker, this will cue a Best Practice Advisory (BPA) to appear for clinic staff during the encounter. This BPA will guide clinic staff in the offer of SmokefreeTXT and allow them to document the patient response (acceptance or decline). If a patient consents to setting a quit day in the next 30 days, indicates that they have a text-capable phone, and accepts the referral, the provider will place an order for the text-capable phone to receive SmokefreeTXT messages. SmokefreeTXT will send terms of use (including a notice that text messaging fee rates may apply) and privacy practice information to the identified phone upon receipt of the eReferral. Patients have the option to stop receiving SmokefreeTXT messages at any time by texting "STOP" to SmokefreeTXT. Text messages may use patient cell-phone service plan minutes. Patients will be advised of this by SmokefreeTXT upon enrollment. Patient records in the EHR will be automatically update with the result of the eReferral 6 weeks after the target stop-smoking date (set at enrollment). This may be up to 10 weeks post-referral (as the target stop-smoking date could be set up to 30 days after eReferral) and will indicate whether the patient stayed enrolled, dropped out (by texting "STOP"), and reported any smoking in the past 7 days at the 6-week post-quit follow-up. No medications will be provided by SmokefreeTXT, so there will be no need to update the patient medication list in the EHR.

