#### **Specific Aims:**

This UW-CTRI study is designed to assess whether completely electronic, EHR-based, closed-loop referrals for tobacco cessation (eReferral) from primary care clinics to a state telephone tobacco quitline can increase the number/percentage of adult tobacco users receiving evidence-based tobacco dependence treatment when compared to paper-based, manual fax referrals.

2/28/2017 Amendment: The specific aim of this extension of the protocol is to evaluate the extent to which electronic, closed-loop eReferral to SmokefreeTXT in up to 3 primary care clinics engages patients who smoke in the program, retains these individuals in the 6-week duration of the program, and helps them to quit smoking as assessed via self-report at the end of the 6-week program.

**Primary Aim 1:** To evaluate the rates of referral of tobacco users visiting primary care clinics to the WTQL, comparing those who were referred via an EHR-based electronic referral system vs. those referred via a manual paper fax referral system. Analyses will address the change in referrals from pre- to post-intervention and the trajectory of referral post-intervention per clinic.

**Primary Aim 2:** To evaluate the rates of quality referrals of tobacco users visiting primary care clinics to the WTQL, comparing those who were referred via an EHR-based electronic referral system vs. those referred via a manual paper fax referral system (quality referrals are defined as ones that result in individuals who enroll in and receive WTQL counseling and/or medication treatment services). Analyses will address the change in referrals from pre- to post-intervention per clinic.

2/28/2017 Amendment: The primary aim of the SmokefreeTXT eReferral project is to examine uptake (initial enrollment), retention (continuing engagement through the end of the 6-week program), and effectiveness (in terms of abstinence 6-weeks after the target stop-smoking date) of eReferral to SmokefreeTXT among primary care patients referred by clinic staff during clinic visits.

**Secondary Aim 1:** To examine variation in referral rates across clinics to test the hypothesis that the eReferral system will result in greater consistency in referral in addition to higher rates of referral. Nonquantitative methods will be used to understand the sources of variation.

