## I. Methods for Evaluating the eReferral Mechanism

The study will include three phases (see Table 1):

- 1) The Preparation Phase (3 months): 24 clinics (12 clinics/system) are to participate in the randomized clinical trial. Clinics will meet inclusion criteria (see below), and generate baseline rates of manual paper fax referral of adult tobacco users to the WTQL. These will be calculated for the prior 6-12 months, and the 24 clinics that will participate in the clinical trial will be randomized to two different WTQL referral mechanisms (twelve to use the manual F2Q mechanism, and twelve to transition to the eReferral mechanism). Also during this phase, the eReferral procedures and technology will be tested in one clinic within each system for one to three months. The technology will be adapted as needed. These pilot clinics will not be involved in the research.
- 2) The Study Implementation Phase (12 months): Staff in all 24 clinics will receive a baseline 30 minute in-person training, regarding either the paper or electronic referral to the WTQL (based on their randomization). While some of the clinics randomized to the paper referral system will have already received training on this referral mechanism at some time in the past (when the system was implemented in that clinic or refreshed), we will provide a refresher training on F2Q referral for all clinics in this condition consisting of about the same amount of time as used in the eReferral training. An UW-CTRI Outreach Specialist will lead all trainings and a member of the research team will also be present. All Medical Assistants, Nurses, Clinician Providers (physicians, nurse practitioners, and physician assistants), and Clinic Managers will be asked to attend the training. For any staff member who misses the initial training, a second training will be scheduled and data collected on the proportion of all staff who attended either of the trainings.

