are specific to SmokefreeTXT. We are only asking about experience referring patients to SmokefreeTXT after study launch because we expect very few clinical staff to have knowledge of or experience with SmokefreeTXT prior to eReferral training and launch. Clinics in the existing protocol had experience with fax-to-quit programs for Quitline referrals, but have no such history with SmokefreeTXT or other text-message-support programs for smoking cessation.

9/19/2019. The items in the survey have not been changed, but items that previously only applied to clinicians now apply to rooming staff who will make the SmokefreeTXT referral offer to patients.

Dependent Variables for Intervention Phase: Acquisition & Appraisal: The tobacco quitline vendor (Optum) will derive summary data on an ongoing basis from both the F2Q and the EHR-based referrals with patient specific identifiers removed and provide such summary data to study staff. These summary data forms will allow us to compute the following monthly outcomes linked to clinic: (1) number of referrals to the quitline, (2) number of successful WTQL contacts with patients, and (3) number of quality WTQL contacts with the patient (where the patient enrolls in and receives tobacco quitline services). This quitline information will supplement information provided by the clinic's EHR system (both F2Q and eReferral clinics have identical Epic EHR systems) That is, the number of quitline referrals can be divided by the total number of tobacco users since participating clinics must have accurate estimates of tobacco users seen in each clinic/month to compute a clinic smoker referral rate. Thus, these outcomes will address how many patient tobacco users are *referred* to the quitline each month (via the fax or EHR-based referral mechanism), the number of these referred patients whom the quitline successfully contacts/month, and the number of these patients who enroll in a quitline counseling program/month (quality contacts). We can also determine the proportion of quality contacts by dividing the number of quality contacts by the total contacts. These measures will also be computed on a per month basis by clinic so as to capture such outcomes as contacts/month, quality contacts/month, and referrals/month.

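### The eReferral arm is described both as replacing fax and as adding to it, and nothing in the referral counts ensures that each smoker is counted once

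*Combined protocol and SAP*

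**What the plan says.** The eReferral arm is described in two ways.

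- **Replacement.** The Preparation Phase text assigns the 24 clinics as "twelve to use the manual F2Q mechanism, and twelve to transition to the eReferral mechanism". Clinic Randomization repeats this: six clinics per system continue with fax and six move to the EHR system. After tobacco status has been recorded, the flow-chart text says: "At this point, workflow processes diverge based on whether the clinic was randomized to the F2Q or the eReferral condition". Table 2 treats the arms as alike except for the referral mechanism. The manual section assigns the fax form to F2Q sites and an EHR counterpart to eReferral sites.
- **Addition.** Tobacco User Referral in eReferral Condition says that the eReferral "condition involves all of the procedures and resources used in the F2Q condition above", then: "In addition, the following workflow will be followed for the eReferral clinic site". The procedures directly above, under Tobacco User Referral in F2Q condition, are the paper form left in the exam room, the patient's signature and the fax: "The form is then passed to the MA (part of the visit closure workflow procedures) who then faxes the form to the WTQL".

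On counting, Dependent Variables for Intervention Phase says the quitline vendor will "derive summary data on an ongoing basis from both the F2Q and the EHR-based referrals with patient specific identifiers removed". The monthly number of referrals is one of the resulting outcomes, and it is divided by tobacco users seen. The later text on data acquisition confirms that referral rates come from the quitline's monthly reports. The Hypotheses & Analytic Plan instead defines a yes/no outcome for each smoker and compares the 12 control with the 12 experimental clinics. Primary Aim 1 is worded by route: "comparing those who were referred via an EHR-based electronic referral system vs. those referred via a manual paper fax referral system".

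**The concern.** The trial asks how electronic referral compares with fax referral. If eReferral clinics keep the fax route open, the contrast becomes two routes against one. A higher rate would then show the effect of adding eReferral to fax, not of using it in place of fax. That limit on interpretation would remain even with perfect counting.

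The counting issue is separate. If the numerator is the number of referrals received, a smoker who is both faxed and eReferred contributes two. Repeat referrals by one route can occur in either arm. Cross-route duplicates need both routes, so they can occur only in the eReferral arm and would push the primary comparison in one direction.

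**Working it through.** **1. Is the fax route closed in eReferral clinics?** No section says that it is, or how a fax from such a clinic is handled. Methods Overview says some of these clinics already offer fax referral, and baseline data come from selected clinics that had used it. Continued faxing is therefore possible, but it is not documented.

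**2. Can the per-smoker outcome be built from the data described?**

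| Section | Quantity |
|---|---|
| Dependent Variables; data acquisition text | referrals reported by the quitline ÷ tobacco users seen, per clinic-month, from de-identified summaries |
| Hypotheses & Analytic Plan | each smoker seen: referred or not |

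The two agree only if each referral is a different smoker. A clinic-month count without identifiers does not show whether a fax and an electronic order concern the same person. Only the vendor could match them, before removing identifiers, and no section asks it to.

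**3. The plan's own figure.** Inputs from Power Analyses for Intervention Phase: 2% against 7%, SD 2.5 points, two-sided alpha 0.05, 6 clinics per arm in each of two systems, so 12 per arm. With clinic means as the unit:

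- standard error = 2.5 × √(2/12) = 1.02 points
- noncentrality = 5 / 1.02 = 4.90 on 22 df
- power = 99.7% (noncentral t)

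The section reports its result for 1% against 7%, which gives more than 99.9%. The stated figure of over 90% therefore reproduces for the 24-clinic trial. No intraclass correlation is given, so the program run itself cannot be repeated. Neither issue raised here changes this figure.

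**4. Illustration of duplicates.** The overlap shares are assumptions. Let f be the share of eReferred patients who are also faxed, with both referrals counted. Recorded rate = 7% × (1 + f).

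| f (assumed) | Recorded rate | Difference from 2% |
|---|---|---|
| 0 | 7% | 5 points |
| 10% | 7.7% | 5.7 points |
| 25% | 8.75% | 6.75 points |
| 50% | 10.5% | 8.5 points |
| 100% | 14% | 12 points |

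The last two rows imply fax counts of 3.5% and 7% of smokers in eReferral clinics, above the 2% planned for the F2Q arm. They are outer bounds, not expectations.

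**5. Illustration with no true difference.** Suppose both arms refer 2% of smokers and a share f of the eReferral-arm patients is sent twice. The spurious difference is 2 × f points. With the standard error from step 3, the two-sided rejection probability is:

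- f = 25%: 0.5 point, 7.6%
- f = 50%: 1.0 point, 15.5%
- f = 100%: 2.0 points, 46.6%

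The nominal level is 5%. These use a t comparison of clinic means, not the planned GEE model. With a true per-smoker outcome, the inflation in steps 4 and 5 is zero.

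**The case against.** Most of the text favours replacement. The sentence about F2Q procedures may mean only the shared training, flow chart, feedback and quitline services. The same section goes on to describe verbal consent recorded in the EHR and an electronic order, which reads as a substitute for the signed and faxed form. It also points to a workflow figure whose content is not available here. This argument largely stands: the conflict is one of wording and does not prove that the arm runs two routes. However, training and feedback are set out in other sections, and what stands directly above the sentence is the fax workflow, so a site could reasonably follow it literally.

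A reader might infer that patients sent by both routes are in fact counted twice. The documents do not support that. The analytic plan's outcome counts a smoker once, and Table 2 and parts of the dependent-variable text also speak of patients or tobacco users referred. What remains is that the described data feed does not secure this definition.

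A reader might also infer, by carrying the planned 2% fax rate into the eReferral clinics, that 2 of the 5 planned points are not an eReferral effect. The documents give neither a fax rate for those clinics nor an overlap. If the routes did not overlap, 5% electronic plus 2% fax against 2% fax would still leave a 5-point difference from the electronic route.

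Finally, Aim 1's wording by route does not mean that the analysis ignores randomisation. The analytic plan already compares clinics by condition, and fax forms are clinic-specific, so a stray fax can be traced to its clinic.

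**Conclusion.** Two limited points hold. First, the description of the eReferral condition conflicts with the Preparation Phase, Clinic Randomization, Table 2, manual and flow-chart text; taken literally, it changes the contrast to fax plus eReferral against fax alone. Second, the rate defined from de-identified referral counts does not guarantee the per-smoker outcome in the analytic plan, so repeat or cross-route referrals could be counted more than once, the latter only in the eReferral arm.

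The size of any bias is unknown. It is zero if smokers are truly counted once. Otherwise it depends on an overlap that the documents do not give, and the figures for f above zero are illustrations only. The issue is worth settling because the primary outcome depends on it and the remedy is cheap.

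**What to change.** - Reconcile the opening of Tobacco User Referral in eReferral Condition with the Preparation Phase, Clinic Randomization and flow-chart text. State whether fax remains available in eReferral clinics and how a fax from one is handled. Which arrangement applies is for the sponsor to say.
- In Dependent Variables and the data acquisition text, define the numerator as unique tobacco users referred per clinic-month by any route, de-duplicated by the vendor before identifiers are removed, to match the analytic plan.
- Align the route-based wording of Primary Aim 1 with the planned comparison by randomised condition.
- Tabulate fax and electronic counts separately for the eReferral clinics.

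The cost is protocol wording and a small addition to the vendor's monthly report. The eReferral rate may come out slightly lower if duplicates exist. The sample size does not change.
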